**Abstract:**

Immediate postpartum initiation of the etonogestrel contraceptive implant has been proven to decrease rates of rapid, repeat pregnancies. Evidence supports that in healthy women with term infants initiation of the contraceptive implant 1-3 days postpartum does not appear to have any adverse effects on lactogenesis or breastfeeding continuation. However, no high quality study to date has examined the effects of progestin-only contraception in women known to be at risk for low milk supply, including women with a premature delivery, obesity, polycystic ovarian syndrome, diabetes, or a prior history of low milk supply.

Our goal is to measure the impact of timing of postpartum contraceptive implant insertion on breastfeeding success and duration. This will be a three-armed randomized non-inferiority study of women who plan to breastfeed, have known risk factors for low milk supply, and who intend to use the contraceptive implant postpartum. Women will be randomized to one of three groups for the timing of contraceptive implant placement: within 30 minutes of placental delivery, 24-72 hours postpartum, or 6 or more weeks postpartum. Women will be assessed at 6 weeks, 3 months and 6 months postpartum. Outcomes will include time to lactogenesis II, duration and exclusivity of breastfeeding, continuation of and satisfaction with the contraceptive implant, and side effects, including bleeding patterns, associated with the implant.

Findings from this trial will be used by clinicians, hospital systems, and policy makers working to expand access to immediate postpartum implants while supporting women in meeting their breastfeeding goals.

## Specific Aims

Our goal is to measure the impact of timing of postpartum contraceptive implant insertion on breastfeeding success and duration and to explore women's experiences with and attitudes towards contraceptive and breastfeeding counseling in the peripartum time period.

Specific Aim 1: To compare time to lactogenesis stage II among women randomized to receive the contraceptive implant within 30 minutes postpartum, 1-3 days postpartum and 6 or more weeks postpartum, utilizing a validated measure

Specific Aim 2: To assess rates of breastfeeding continuation, exclusivity, and satisfaction as well as device continuation and method satisfaction at 6 months postpartum among women who were randomized to receive the contraceptive implant within 30 minutes postpartum, 1-3 days postpartum and 6 or more weeks postpartum, utilizing a validated measure

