Women will be enrolled, consented and randomized on Labor and Delivery, prior to delivery. The study brochure will be included in the standard educational materials provided to all women on admission to Labor and Delivery. All enrollment and screening will be done in private labor and delivery rooms and all measures will be taken to ensure patient privacy. Women will be explicitly told that their participation in this trial is voluntary and that they have the option of receiving a contraceptive implant at any of the time points included in this study if they decline participation in this trial. Only co-investigators who have completed CITI training and who are intimately familiar with the study protocol will be approaching or enrolling patients into the trial.

During the informed consent process, women will receive standardized contraceptive counseling, including information about the contraceptive implant and its potential effects on breastfeeding. Women who are eligible for the trial and interested in participating will be enrolled and randomized in a 1:1:1 ratio to one of the three groups to determine their timing of contraceptive implant placement. Participants will be assigned using computer-generated random numbers in blocks of varying sizes with strict allocation concealment using sequentially numbered opaque envelopes. Women will be informed of their randomization group at the time of enrollment into the trial.

Women randomized to receive the implant within 30 minutes of delivery will have the implant placed in the delivery room or operating room within 30 minutes of placental delivery. Placement of the implant will not interfere with any skin-to-skin interactions that are currently routinely encouraged for the mother and infant after every delivery. Women randomized to receive the implant within 1-3 days of delivery will have their implant placed on the postpartum unit more than 24 hours after delivery, but prior to discharge from the hospital. Women randomized to receive the implant at 6 or more weeks postpartum will be scheduled for an outpatient visit with the family planning clinic at 6-8 weeks postpartum for implant placement.

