#### *Study Procedures*

Follow-up and data collection for participants in all three groups will be identical. In order to achieve specific aim 1, time to lactogenesis stage II will be measured based on maternal perception based on measures described and validated by Chapman et al and utilized in a similar study by Gurtcheff et al. Beginning on the first postpartum day,

subjects will be contacted daily. Subjects will be asked, "Has your milk come in? Some women experience this as a prickly feeling or tingling in the breast, dripping from the other nipple when nursing, milk running from the baby's mouth, or gulping by the baby." If the response is positive, women will then be asked, "When did your milk come in?" and the response recorded to the nearest hour. If lactogenesis has not occurred prior to hospital discharge, the patient will be contacted at least daily by their preferred method (phone, text or email) from study personnel until lactogenesis can be confirmed and recorded.

To achieve specific aim 2, women will complete study follow-up questionnaires at 6 weeks, 3 months and 6 months postpartum either by phone interview or by electronic web-survey, depending on the participant's preference. These questionnaires will assess breastfeeding status, exclusivity and satisfaction as well as contraceptive method continuation, satisfaction, and side effects, including bleeding. Women will be asked to contact the study coordinators when they stop breastfeeding or if they discontinue the contraceptive implant.

*Recruitment, Follow-up and Retention.*

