Successful recruitment, follow-up and retention represents the most significant challenge to the completion of this project. The population of women we intend to enroll is socioeconomically disadvantaged and has high rates of non-adherence to postpartum care. Only 43% of women who deliver at Weiler attend a postpartum visit within 12 weeks of delivery. While this is a difficult to study population, they are also the women who may benefit the most from access to immediate postpartum contraception as attendance at a postpartum visit clearly represents a significant barrier to care for most of these women. [name] has a proven track record of successfully following women in this specific community in the immediate postpartum period. She served as the principal investigator on a set of trials examining the effects of a primary care intervention on breastfeeding outcomes. During these trials she successfully recruited and followed a cohort of postpartum women from our institution and has developed a set of proven strategies for ensuring high levels of retention among a population of women with historically high attrition rates. We intend to use the following specific strategies:

- 1) Strong Rapport with the Participants

- a) Research Coordinators (RC) will visit the women enrolled in to the study at least twice during their postpartum admission to encourage rapport building
- b) RCs will maintain regular contact with participants throughout the follow up period via text and email. Reminders will be emailed and texted in the weeks prior to any scheduled follow-up.
- c) RCs will send birthday ECards for all the study participants.
- d) Participants will be provided with business cards and other items (pens, magnets) containing the RC cell phone number and study contact information.

2) Convenience for the Participants

- a) Brief- Upon final pilot testing the follow-up questionnaires will take < 15 minutes to complete.
- b) Flexible methods- Participants will have the option of completing the follow-up questionnaires via phone or web survey.
- c) Flexible hours- Women will indicate their preferred times to be called, including nights and weekends
- d) Bilingual- All written study materials will be available in both English and Spanish. The RCs will be bilingual.

3) Educational and Appropriate Materials and Questionnaires

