#### *Sample Size*

To achieve specific aim 1, we chose a non-inferiority margin of an additional 8 hours to achieve lactogenesis II, as this would be clinically relevant. In order to achieve 80% power, using a one-sided Type 1 error of 5%, and with a standard deviation in time to lactogenesis of up to 18 hours, 63 women would be needed in each group, for a total of 189 women.

To achieve specific aim 2, larger sample size will be required. Prior studies in our population have found that breastfeeding continuation rates at 6 months postpartum are 27%. Assuming a non-inferiority margin of 15%, to achieve 80% power using a one-sided Type 1 error of 5%, we would need to enroll 109 women per group, for a total of 327 women total. Assuming a 15% loss to follow up rate, we will enroll 375 women total, 125 in each group. This recruitment goal will be met over an 18 month time period and is attainable based on the approximately 60 implants placed each month on the Labor and Delivery and Postpartum units.

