#### *Analysis Plan*

The following outcomes will be evaluated using T-tests and include: exclusive breastfeeding continuation, any breastfeeding continuation, implant continuation. Additional secondary outcomes include side effects and tolerability of the implant, vaginal bleeding patterns, and contraceptive use. To evaluate these secondary outcomes between the two groups we will use the T-test, Wilcoxon Rank Sum test, Chi-squared test, or Fisher's exact test as appropriate.

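### Does implant continuation at 6 months need a written denominator and a rule for women who never receive the implant?

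*Combined protocol and SAP*

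**What the plan says.** Specific Aim 2 lists "device continuation and method satisfaction at 6 months postpartum among women who were randomized" to the three timings. The Abstract describes the outcome as "continuation of and satisfaction with the contraceptive implant". The Analysis Plan names "any breastfeeding continuation, implant continuation" among the outcomes to be tested, and lists contraceptive use separately as a further secondary outcome. It names no analysis set for any outcome.

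Under Recruitment, the first arm is inserted in the delivery or operating room. The second is inserted "more than 24 hours after delivery, but prior to discharge from the hospital". The third "will be scheduled for an outpatient visit with the family planning clinic at 6-8 weeks postpartum for implant placement".

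Continuation is learned from the questionnaires at 6 weeks, 3 months and 6 months and from self-report: "Women will be asked to contact the study coordinators when they stop breastfeeding or if they discontinue the contraceptive implant". The section on follow-up and retention warns: "Only 43% of women who deliver at Weiler attend a postpartum visit within 12 weeks of delivery". Sample Size states: "Assuming a 15% loss to follow up rate, we will enroll 375 women total, 125 in each group".

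**The concern.** The word continuation can be read in two ways, and they answer different questions.

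- **All randomised women.** A woman who never had the implant counts the same as one who had it removed. Because only the delayed arm depends on an outpatient visit, missed visits there could be reported as women giving up the implant. The arm inserted before discharge can also lose some insertions, but probably fewer.
- **Inserted women only.** This separates removal from non-receipt. However, it compares groups selected after randomisation, and by 6 months postpartum the delayed group has had at most 18 to 20 weeks of exposure (26 minus 8, or 26 minus 6) against about 26 weeks in the early groups.

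If the reading were chosen after the data were seen, the estimate could move and might change sign. The trial is meant to inform access to immediate postpartum implants, so a mislabelled difference in continuation could mislead its readers.

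**Working it through.** **The plan's own figures.** None concerns implant continuation. Both sample sizes reproduce with (1.645 + 0.842)² = 6.18:

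- Aim 1: 2 × 18² × 6.18 / 8² = 62.6, so 63 per group.
- Aim 2 (breastfeeding): 2 × 0.27 × 0.73 × 6.18 / 0.15² = 108.3, so 109 per group.

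The point therefore touches neither calculation.

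**Inputs for the outcome in question.** From the documents: 125 per arm, 15% loss (125 × 0.85 = 106 evaluable), and delayed insertion at 6 to 8 weeks. Assumed, because the documents give no values: removal r of 10% or 20% by 26 weeks after insertion, the same in every arm and at a constant rate; early uptake Ue of 100% or 95%; delayed uptake Ud of 80% or 90%.

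**Formula.** The proportion still in place w weeks after insertion is S(w) = (1 − r)^(w/26).

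| r | S(26) | S(20) | S(18) |
|---|---|---|---|
| 10% | 0.900 | 0.922 | 0.930 |
| 20% | 0.800 | 0.842 | 0.857 |

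**All-randomised reading.** Early minus delayed = Ue × S(26) − Ud × S(18 to 20), in percentage points:

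| Ue | Ud | r = 10% | r = 20% |
|---|---|---|---|
| 100% | 80% | 15.6 to 16.2 | 11.5 to 12.6 |
| 100% | 90% | 6.3 to 7.0 | 2.9 to 4.2 |
| 95% | 80% | 11.1 to 11.7 | 7.5 to 8.6 |
| 95% | 90% | 1.8 to 2.5 | −1.1 to 0.2 |

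The unpooled 95% half-width with 106 per arm is 9.1 to 12.1 points across these cases.

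**Inserted-only reading.** S(26) − S(18 to 20) = −2.2 to −3.0 points (r = 10%) or −4.2 to −5.7 points (r = 20%). The sign is opposite, and the difference comes wholly from the shorter exposure. With 106 early women and 85 or 95 inserted delayed women (106 × 0.80 or 0.90), the 95% half-width is about 8 to 11 points, so this difference would usually not be distinguishable from zero.

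**Low uptake.** The 43% attendance figure covers all women delivering at the hospital. It is not expected uptake among trial participants, who are paid and actively followed. Taken as an extreme, 125 × 0.43 = 54 inserted and 71 never inserted. If 80% to 95% of inserted women in every arm still had the implant, and all early women were inserted, the all-randomised gap would be 0.80 − 0.43 × 0.80 = 46 points, up to 0.95 − 0.43 × 0.95 = 54 points. This simpler version ignores the exposure difference, so the inserted-only gap is zero.

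**What the gap represents.** In every case the all-randomised difference is the effect of assigned timing on having an implant in place at 6 months. It is not a biased estimate of that quantity. It misleads only if it is described as removal, and the number inserted in each arm shows a reader which it is.

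**The case for a change.** The strongest case for a change is that the reference to randomised women in Aim 2 may only identify the arms compared. The same phrase governs method satisfaction, which a woman without the implant cannot rate, and both the Abstract and the request to report discontinuation lean towards women who had one. Even on the literal reading, no rule for never-inserted women is written. Non-receipt follows from the assigned timing, so it will not balance out across arms, and a choice made after unblinding is open to selection.

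Much of this stands as description: the rule is absent, the imbalance is likely, and the two readings differ. Three things limit it.

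- Contraceptive use is listed separately, so the plan already intends to look at use as well as continuation, although that outcome is undefined too.
- The change of sign rests on an inserted-only difference smaller than its own margin of error.
- The absence of a rule for women lost to follow-up applies to every outcome in the Analysis Plan, so it adds no weight here. This is so even though it could matter numerically: at 100% early and 80% delayed uptake, the complete-case gap falls from 11.5–16.2 points to between −0.6 and 3.2 if all the delayed arm's 15% loss falls on never-inserted women.

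More elaborate rules would not clearly do better. Counting lost women with no recorded insertion as non-users, for example, would misclassify any who were inserted elsewhere, most plausibly in the delayed arm.

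**Conclusion.** No change to the plan is needed. This is a definition left unwritten for a secondary outcome. An analyst following the literal wording of Aim 2 would compare implant in place at 6 months across assigned arms, count never-inserted women as not using it, show how many were inserted, and treat removal among inserted women as descriptive. The commitment to CONSORT in Research Design and Study Subjects supports reporting denominators and receipt of the assigned intervention by arm; what that guideline asks for is general knowledge rather than text in these documents, and the conclusion does not depend on it.

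The size and direction of any distortion cannot be settled from the documents: about −1 to 16 points on the all-randomised reading under the assumed uptake and removal, more if delayed uptake is much lower, and 2 to 6 points the other way among inserted women. Neither sample size nor either breastfeeding aim is affected. The conclusion assumes that the by-arm result is described as implant use and that insertion counts are reported beside it.

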## **Research Design and Methods**

### *Research Design and Study Subjects*

This will be a three-armed randomized non-inferiority study of women delivering at the Weiler Hospital of the Albert Einstein College of Medicine who plan to breastfeed, have known risk factors for low milk supply, and who intend to use the contraceptive implant postpartum. Women will be randomized to one of three groups: device placed within 30 minutes of placental delivery, 24-72 hours postpartum, or 6 or more weeks postpartum. All study activities will adhere to the CONSORT guidelines for reporting randomized trials. Women will be assessed at enrollment, 1-5 days postpartum, 6 weeks, 3 months and 6 months postpartum.

Eligibility Criteria will include:

- 1) Live pregnancy of at least 24 weeks gestation
- 2) Intention to use a contraceptive implant postpartum
- 3) Intention to use a non-hormonal bridging method of contraception until a contraceptive implant can be placed
- 4) 18 years of age or older
- 5) English or Spanish speaking
- 6) Women will be enrolled either during prenatal care or upon admission to Labor and Delivery.
- 7) Absence of pain. Among women who are being enrolled on Labor and Delivery MUST fall into one of the three following categories:

- Women presenting for induction of labor. Women will be approached and enrolled prior to the onset of labor.
- Women presenting for a planned cesarean delivery. Women will be approached and enrolled prior to entry into the operating room.

- Women who have an Epidural in place for management of pain. Prior to engaging in a discussion regarding the study protocol, women will be asked if they are experiencing any pain, and if the answer is yes, they will not be eligible for entry into the study.

7) Presence of at least one of the following conditions known to be a risk factor for low milk supply:

- Expected delivery prior to 37 weeks
- Obesity (pre-pregnancy BMI >35)
- Polycystic Ovarian Syndrome
- Diabetes (gestational or pre-gestational)
- Self-reported difficulty with low milk supply in past

*Setting and Population*

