#### Adverse Event Reporting Period

The study period during which adverse events must be reported is normally defined as the period from the initiation of any study procedures to the end of the study treatment follow-up. For this study, the study treatment follow-up is defined as 6 months postpartum.

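### Implant outcomes are timed from delivery, so contrasts with the delayed arm mix timing of insertion with length of use and uptake and do not measure tolerability

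*Combined protocol and SAP*

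**What the plan says.** The three arms are defined in Research Design and Study Subjects as "device placed within 30 minutes of placental delivery, 24-72 hours postpartum, or 6 or more weeks postpartum". The Recruitment section places the second arm's implant "more than 24 hours after delivery, but prior to discharge from the hospital". It books the third arm into an outpatient clinic at 6–8 weeks; no latest insertion time is given.

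Study Procedures states that "Follow-up and data collection for participants in all three groups will be identical" and that "women will complete study follow-up questionnaires at 6 weeks, 3 months and 6 months postpartum". These questionnaires cover "contraceptive method continuation, satisfaction, and side effects, including bleeding" as well as breastfeeding. Under Adverse Event Reporting Period, "the study treatment follow-up is defined as 6 months postpartum". No assessment is timed from insertion.

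Specific Aim 2 sets the device comparison as "device continuation and method satisfaction at 6 months postpartum among women who were randomized". The Analysis Plan assigns t-tests to implant continuation and adds: "Additional secondary outcomes include side effects and tolerability of the implant, vaginal bleeding patterns, and contraceptive use". For these it lists the t-test, Wilcoxon, chi-squared or Fisher's exact test, and it speaks of two groups although there are three. It does not say whether continuation is counted among all randomised women or only those with an implant placed, nor from what date, and it makes no allowance for length of use.

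**The concern.** At any date counted from delivery, a woman in the delayed arm has used the implant for less time than a woman in either early arm, or has not yet received it. Removals and cumulative side-effect counts build up with use. A difference between the delayed arm and an early arm can therefore come from three sources that the plan does not separate: when the implant was inserted, how long it has been in place, and whether it was inserted at all.

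The 6-week questionnaire is the extreme case. A delayed-arm woman treated per protocol has no implant then, or is only just receiving one, so a contrast on implant side effects would set users against non-users.

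The protocol expects its findings to inform guidelines and policy on postpartum implant use. A continuation or side-effect difference is likely to be read as a statement about tolerability of early insertion, and the planned comparison cannot support that reading in either direction.

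**Working it through.** **The plan's own figure.** No target is stated for any device outcome. The Aim 2 sample size rests on breastfeeding continuation and reproduces: (1.645 + 0.842)² × 2 × 0.27 × 0.73 / 0.15² = 108.3, rounded up to 109 per group. It does not depend on this point.

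**Step 1: length of use.** Weeks of use = assessment week − insertion week. I take 3 months as 13 weeks, 6 months as 26 weeks, and both early arms as week 0, since they differ by at most three days. The delayed arm is inserted at week 6 to 8.

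| Questionnaire | Early arms | Delayed arm | Delayed as share of early |
|---|---|---|---|
| 6 weeks | 6 weeks | 0 weeks | 0% |
| 3 months | 13 weeks | 5–7 weeks | 38–54% |
| 6 months | 26 weeks | 18–20 weeks | 69–77% |

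Insertion at week 12, which the arm definition allows, leaves 14 of 26 weeks (54%) at 6 months.

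**Step 2: removals among women who received an implant.** The documents give no removal rate, so I assume that a share q of users has the implant removed by 26 weeks of use, at the same constant rate in every arm. Expected removals after w weeks are 1 − (1 − q)^(w/26).

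| q (early arms) | Delayed, inserted week 6 (20 weeks of use) | Delayed, inserted week 8 (18 weeks of use) | Gap in points, no timing effect |
|---|---|---|---|
| 10% | 7.8% | 7.0% | 2.2–3.0 |
| 20% | 15.8% | 14.3% | 4.2–5.7 |

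If the whole arm were inserted at week 12, the figures would be 5.5% and 11.3%, giving gaps of 4.5 and 8.7 points. Counted over equal time from insertion, the gap is zero by construction.

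**Step 3: continuation among all randomised women.** Let u be the share of the delayed arm that has an implant placed, and assume all early-arm women have one. Delayed-arm continuation is u × (1 − q)^(w/26), against 1 − q in an early arm. The two are equal when u = (1 − q)/(1 − q)^(w/26):

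- q = 10%: 0.900/0.922 = 97.6% (week 6) and 0.900/0.930 = 96.8% (week 8).
- q = 20%: 0.800/0.842 = 95.0% (week 6) and 0.800/0.857 = 93.4% (week 8).

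Below these uptakes the delayed arm looks worse. The section on Recruitment, Follow-up and Retention reports that only 43% of women delivering at the hospital attend a postpartum visit within 12 weeks. Trial uptake may well be higher, so 43% serves only as an illustrative low end. With q = 10%:

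- u = 85%: continuation is 78.4–79.0% against 90%, or 11–12 points worse.
- u = 43%: continuation is 39.7–40.0% against 90%, or about 50 points worse.

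**Step 4: satisfaction, bleeding and current side effects.** The documents give no time course for these, so no calculation of direction is possible.

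**The case against.** A reader might infer that the delayed arm will look better on every device outcome, so that Aim 2 is biased in favour of delayed insertion. The documents do not support this. Aim 2 refers to women who were randomised, and step 3 shows that on that denominator a modest shortfall in delayed insertion reverses the sign for continuation. For satisfaction and bleeding the direction is open. If side effects cluster soon after insertion, women at 18–20 weeks of use could report more current symptoms than women at 26 weeks.

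Three further points can be made for the plan.

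- A comparison at a fixed time after delivery among all randomised women is a legitimate policy question. That stands, and the measure should be kept. It answers a question about uptake and use, however, not about tolerability.
- The size is moderate. At 6 months on-schedule exposure is 69–77% of the early arms'. With 109 women per arm, 10% against 7.0% has a standard error of √[(0.10 × 0.90 + 0.07 × 0.93)/109] = 3.8 points, and 20% against 14.3% has 5.1 points. The gaps of 2–6 points are thus roughly 0.6 to 1.1 standard errors. This also stands, but a systematic gap of that size still distorts an estimate.
- The Analysis Plan does not say at which questionnaire side effects are compared, so the 6-week contrast is a possibility and not a stated analysis. That is correct; nothing in the plan rules it out.

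**Conclusion.** The concern holds in a limited form. The imbalance in implant use follows directly from the schedule: total at 6 weeks, large at 3 months, and 23–31% less use at 6 months for on-schedule insertion. The Analysis Plan has nothing to separate it from timing or uptake.

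The gap of 2–6 points in removals applies only to women who received an implant. It rests on assumed removal of 10–20% by 26 weeks, a constant rate equal across arms, and insertion at 6–8 weeks. Among all randomised women the sign would probably be reversed; how far depends on delayed-arm uptake, which the documents do not give. No direction can be stated for satisfaction or bleeding.

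This should be changed, because the device outcomes are named in Aim 2 and a better analysis is available at little cost. It does not touch lactogenesis, the breastfeeding outcomes, the sample size, or the contrast of 30 minutes with 24–72 hours.

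**What to change.** 1. Record insertion and removal dates for every woman. Women are already asked to report discontinuation, but the protocol does not list insertion date as a collected item, so it should be named.
2. Report implant placement, and implant use at 6 months postpartum, among all randomised women, labelled as a measure of uptake and use.
3. Separately, analyse time from insertion to removal among recipients by Kaplan–Meier, censored at end of follow-up and compared over the common length of use of about 18 weeks. Label it supportive, because restricting to recipients is not fully protected by randomisation.
4. Do not interpret a 6-week contrast of the delayed arm with the early arms as implant side effects.
5. Present side effects, bleeding and satisfaction descriptively with weeks since insertion.

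The cost is one or two data fields and a revised Analysis Plan paragraph, with no change to sample size or visits. A limit remains on item 5. Early-arm questionnaires fall at about 6, 13 and 26 weeks of use and delayed-arm ones at 5–7 and 18–20, so none of the early arms' falls near 18 weeks. Matching the early arms' 6-week reports with the delayed arm's 3-month reports would leave time since delivery different. The plan should say so.
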